9.2.1.3 Other Efficacy Analysis

If the result of the key secondary efficacy analyses based on the BK ITT and overall ITT Populations are both statistically significant, a formal hypothesis test will be conducted sequentially of the first other secondary endpoint, number of days in the hospital, based on the BK ITT Population. The analysis will be performed using a linear regression model with terms for treatment and the stratification factors at randomization. This secondary endpoint will be tested at the one-sided 0.025 alpha level. Sensitivity analyses will be performed based on the BK mITT and BK PP Populations.

If the result of the analysis based on the BK ITT Population is statistically significant, a formal hypothesis test of this endpoint will be conducted based on the overall ITT Population using a 0.025 alpha level. A sensitivity analysis will be conducted using the mITT Population.

The sequential testing described above will control the overall Type I error for these endpoints at the one-sided 0.025 level.

Other continuous and categorical efficacy endpoints (including secondary and exploratory endpoints not selected for hierarchical testing above) will be summarized descriptively by treatment groups using appropriate populations. Categorical endpoints will be summarized using the number and percentage of participants within each category.

Time-to-event endpoints will be summarized using Kaplan-Meier estimates. In addition, the hazard ratio along with the 95% confidence intervals for the true hazard ratio will be calculated using a Cox proportional hazards model with treatment, stratification factors at randomization, and other potentially confounding factors.

There is no adjustment for multiplicity in the analyses of these other efficacy endpoints.

9.2.2 Analysis of Safety

The safety profile will be based on treatment-emergent adverse events (TEAEs) and changes in vital signs, physical examinations, clinical laboratory assessments, and ECGs. All safety analyses will be based on the Safety Population.

Safety analyses in general will be descriptive and will be presented by phase and treatment group in tabular format. Categorical endpoints will be summarized using the number and percentage of participants within each category. Continuous endpoints will be summarized descriptively with summary statistics (number, mean, standard deviation, standard error, median, first quartile, third quartile, minimum, and maximum).

A TEAE is defined as an adverse event with onset after the start of study treatment (PSL or placebo). The number and percentage of participants with TEAEs will be tabulated by MedDRA System Organ Class and Preferred Term for each treatment group and by severity and relationship to treatment. Adverse events leading to discontinuation of the study and SAEs will be summarized by treatment group. By-participant listings will also be provided for any deaths, SAEs, and adverse events leading to discontinuation of the study.

The key safety endpoint for this study is the incidence and severity of acute GVHD. The incidence and severity of acute GVHD, chronic GVHD, and CRS, and the corresponding exact binomial confidence intervals with 95% confidence level will be presented by treatment group.

Descriptive statistics will be provided for clinical laboratory data, vital sign data, and ECG parameters, presented as both actual values and changes from baseline over time. Abnormal physical examination findings will be presented in a by-participant data listing.

9.2.3 Interim Analysis

An interim analysis will be conducted by an independent unblinded statistician and reviewed by the independent DSMB. This analysis will be based on primary efficacy endpoint data for the first 60 participants randomized in the BK ITT Population. The interim analysis will be for purposes of potentially stopping early for success and for futility. If the study is not stopped based on the interim analysis, then accrual to the study will continue until there are 105 participants in the BK ITT Population.

9.2.3.1 Interim Analysis for Stopping Early for Success

The interim analysis for stopping early for success will be performed based on the primary efficacy endpoint using the method of Pocock. At the interim analysis, if the one-sided p-value from the stratified log-rank test comparing treatment to control is less than 0.0147 (overall alpha = 0.025 adjusted for the interim analysis), the study will be stopped early for success. If the study is stopped early for success based on the primary efficacy endpoint, the key secondary efficacy endpoints and the first other secondary efficacy endpoint will be tested sequentially as described above using a one-sided 0.025 alpha level.

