9.2.1 Analysis of Efficacy

9.2.1.1 Primary Efficacy Endpoint Analysis

The primary endpoint is the time to resolution of macroscopic hematuria in participants with documented BK viruria. Resolution of macroscopic hematuria is defined as resolution to Grade 0 or 1 on the Bedi scale⁴⁷ on 2 consecutive urine assessments \geq 2 days apart without continuous bladder irrigation or nephrostomy tubes; Grade 1 requires confirmation of resolution by urinalysis results of \leq 100 RBCs/HPF. If a participant has nephrostomy tubes that are capped, Bedi assessments may be performed, including for the purpose of assessing for resolution.

The objective is to demonstrate the superiority of PSL therapy to placebo with respect to the time to resolution of macroscopic hematuria.

The primary efficacy analysis will be conducted after all participants have completed 24 weeks of follow up or discontinued from the study. At the primary analysis, the PSL group will be compared to the placebo group in the BK ITT Population using a stratified log-rank test based on the stratification factors at randomization. The study will be considered a success if the one-sided p-value from the stratified log-rank test comparing treatment to control is less than 0.0147 (reduced from 0.025 due to inclusion of an interim analysis based on Pocock method). A supplementary efficacy analysis based on the overall ITT Population will also be conducted. Time to resolution will be calculated from the time of randomization to the date of the first resolution of macroscopic hematuria (see Section 7.1). Participants not observed to achieve resolution will be considered censored at their last follow-up for the primary endpoint. Definitive therapies to stop bladder bleeding, such as cystectomy, bladder vessel embolization, cauterization, application of fibrin "glue" preparations, or formalin instillation are permitted but will be considered treatment failures for the primary endpoint of time to resolution of macroscopic hematuria and will be censored at 24 weeks. The detailed censoring rules will be specified in the SAP.

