A supportive analysis of the primary efficacy endpoint will also be conducted, using a Cox proportional hazards model in order to account for additional potential confounders of the treatment effect. The Cox model will include fixed effect terms for randomized treatment assignment, the randomization stratification factors, concomitant antiviral use, and concomitant systemic corticosteroid use.

In addition, analysis of the primary efficacy endpoint will also be performed based on the BK mITT and BK PP Populations as sensitivity analyses. Subgroup analyses will be conducted to compare responses in participants with BKV viruria $<10^7$ copies/mL to those with BK viruria $\ge10^7$ copies/mL, and to evaluate responses in participants who receive concomitant antiviral therapies to those who do not receive these therapies during the study.

If the result of the primary efficacy endpoint (ie, time to resolution of macroscopic hematuria) is statistically significant based on the BK ITT Population, a formal hypothesis test will be conducted sequentially of this same endpoint based on the overall ITT Population using a 0.025 significance level, rather than the Pocock-adjusted 0.0147 significance level used for the primary analysis based on the BK ITT Population. A sensitivity analysis will also be conducted based on the overall mITT Population.

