9.2.1.2 Key Secondary Efficacy Analysis

The key secondary endpoint is the time to resolution of bladder pain as measured by age-appropriate COAs. Resolution of pain is defined as participants achieving a score on the relevant COA that does not exceed "mild pain" (defined in Section 7) without use of prescription pain medications or supportive bladder care.

If the result of the analyses of the primary efficacy endpoint (ie, time to resolution of macroscopic hematuria) is statistically significant based on both the BK ITT and overall ITT Populations, a formal hypothesis test will be conducted sequentially of the time to resolution of bladder pain based on the BK ITT Population in the same manner as described for the primary efficacy analysis of the primary efficacy endpoint, except that a 0.025 significance level will be used. Additional analyses of the time to resolution of bladder pain will also be performed based on the BK mITT and BK PP Populations as sensitivity analyses.

If this result of the analysis of time to resolution of bladder pain based on the BK ITT Population is statistically significant, a formal hypothesis test of this endpoint will then be conducted based on the overall ITT Population using a 0.025 significance level. A sensitivity analysis will be conducted based on the mITT Population.

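### Under the protocol's two-look success rule, testing the later hypotheses at the full one-sided 0.025 does not control Type I error as claimed; the SAP's futility-only interim removes the problem

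*Protocol*

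**What the plan says.** **Primary.** Protocol 9.2.1.1 declares success at the final analysis on a one-sided criterion: "p-value from the stratified log-rank test comparing treatment to control is less than 0.0147 (reduced from 0.025 due to inclusion of an interim analysis". Protocol 9.2.3.1 applies the same boundary at the interim: if the p-value is "less than 0.0147 (overall alpha = 0.025 adjusted for the interim analysis), the study will be stopped early for success".

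**Later hypotheses.** All are tested at the unadjusted level:
- Hematuria in the overall ITT Population (9.2.1.1): "using a 0.025 significance level, rather than the Pocock-adjusted 0.0147 significance level used for the primary analysis".
- Bladder pain in BK ITT (9.2.1.2): "in the same manner as described for the primary efficacy analysis of the primary efficacy endpoint, except that a 0.025 significance level will be used". The overall ITT test of pain follows, also at 0.025.
- Hospital days in BK ITT (9.2.1.3): "This secondary endpoint will be tested at the one-sided 0.025 alpha level". The overall ITT test follows at the same level.
- After an early stop for success (9.2.3.1), the key secondary and first other secondary endpoints "will be tested sequentially as described above using a one-sided 0.025 alpha level".

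**Claim.** Protocol 9.2.1.3: "The sequential testing described above will control the overall Type I error for these endpoints at the one-sided 0.025 level".

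**SAP.** SAP V1.0 (14 November 2023) is later than Protocol v5.0 (23 February 2022). Its interim is for futility only (2.2.1, 3.7). The primary is tested once at one-sided 0.025 (3.4.1), and the same fixed sequence follows at 0.025 (3.4.1 to 3.4.3). The SAP points out that its day numbering differs from the protocol's, but does not point out this change.

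**The concern.** A fixed sequence lets each hypothesis inherit the full level when there is one analysis. With two success looks, the look at which a later hypothesis is tested is chosen by when the primary crosses its boundary. An interim at which the primary looks good tends also to be one at which a positively correlated secondary looks good, so the choice favours rejection. Passing the gate does not turn a two-look procedure into a single-look one; the later hypothesis needs a two-look boundary of its own.

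At stake is whether the error guarantee printed in the protocol is true for the overall ITT claim, the pain claim and the hospital-days claim. The clinically plausible case is a product that clears hematuria but does not relieve pain.

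**Working it through.** **Inputs from the documents.** Boundary 0.0147 per look for the primary (z = 2.178); 0.025 for later hypotheses (z = 1.960); interim on the first 60 of 105 BK ITT participants; medians 12 and 6 weeks (hazard ratio 2), exponential; 10% dropout by 24 weeks; BK ITT assumed to be 85% of those randomized.

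**Assumptions.** The information fraction t is not stated. I use t = 0.50 (the equally spaced Pocock case) and t = 60/105 = 0.571 (a ratio of participants, not events), with the same t for both endpoints. Correlations ρ are not stated, so a range is shown. For ITT against BK ITT, ρ is approximated by √0.85 = 0.92. The allocation ratio is not visible; 1:1 is assumed for the design drift.

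**Step 1: reproduce the plan's figures.** Two equally spaced Pocock looks at overall one-sided 0.025 give a nominal level of 0.0147 per look, as stated. At 0.0147 per look the primary's overall error is 0.0250 (t = 0.50) or 0.0243 (t = 0.571), so the primary itself is controlled. The assumptions in 9.2.4 give 85.5 expected events and power of 84.8% (Schoenfeld, final look only), 86.2 to 86.3% (both looks) or 83.4% (Freedman, both looks), consistent with the stated 83.8% to within about 2.5 points.

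**Step 2: error of a true-null later hypothesis.** Let X1, X2 be the primary statistic at the two looks, with drift δ at the final look, and Y1, Y2 the later statistic under its null. The correlation between looks is √t; that between endpoints is ρ. With critical value d for the later test:

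Error = P(X1 > 2.178, Y1 > d) + P(X1 ≤ 2.178, X2 > 2.178, Y2 > d)

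Strong control requires this to be at most 0.025 for every δ. The design drift is δ = √85.5 × ln 2 / 2 = 3.2.

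**Step 3: results** (each cell: t = 0.50 / t = 0.571).

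| ρ | d = 1.960 (0.025), maximum over δ | d = 1.960, at δ = 3.2 | d = 2.178 (0.0147), maximum over δ |
|---|---|---|---|
| 0 | 0.0250 / 0.0250 | 0.0215 / 0.0216 | 0.0147 / 0.0147 |
| 0.3 | 0.0261 / 0.0257 | 0.0260 / 0.0255 | 0.0154 / 0.0151 |
| 0.5 | 0.0275 / 0.0267 | 0.0271 / 0.0264 | 0.0163 / 0.0158 |
| 0.7 | 0.0296 / 0.0285 | 0.0267 / 0.0259 | 0.0176 / 0.0169 |
| 0.92 | 0.0347 / 0.0332 | 0.0255 / 0.0251 | 0.0208 / 0.0198 |
| to 1 | 0.0416 / 0.0403 | 0.0252 / 0.0250 | 0.0250 / 0.0243 |

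Numerical integration and Monte Carlo (4 million draws) agree. The last row is the ceiling: the chance that a null statistic crosses the fixed value d at either of two looks.

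**Step 4: what the ITT case requires.** At ρ = 0.92 the maximum lies near δ = 1.0, a BK hazard ratio of exp(2 × 1.0 / √85.5) = 1.24. For the overall ITT effect to be null, weighting log hazard ratios 85/15, the other participants would need exp(−0.85 × 0.2163 / 0.15) = 0.29. If BK ITT is also null (δ = 0), the error at ρ = 0.92 is about 0.019.

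**Limits of the model.** It treats the gates between the primary and the later hypothesis as passed, so for pain and hospital days the values are upper values. Section 9.2.3.1 does not say whether follow-up continues after an early success before the secondaries are tested, so the secondary information at that point is unknown.

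**The case against.** The strongest reply is that the plan has already moved on. The SAP is the later document and was due to be finalized before the interim. It has one efficacy test at 0.025 and a non-binding futility rule, which cannot inflate Type I error. Under it the fixed sequence at 0.025 is valid. This stands. A reader might infer that the analysis the SAP prescribes has inflated error; the documents do not support that.

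It is also fair to say that the inflation is modest. The largest figures are maxima over the primary effect, and near the design effect the error is 0.025 to 0.027. A reader might take 0.033 to 0.035 as the expected error of the overall ITT claim. That is not supported either: it needs a modest BK benefit together with strong harm in the remaining 15%, which nothing in the documents suggests. Nor does each secondary get two independent tests at 0.025; it is tested once, at a selected look, which is why the ceiling is about 0.042 and not 0.05.

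On scope, the sentence in 9.2.3.1 names only the key secondary and first other secondary endpoints. The level for ITT hematuria is set in 9.2.1.1 and reaches the early-stop case only through the reference back to the sequence described above.

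What the reply leaves standing is that the protocol still contains the success look, the 0.0147 boundary and an unqualified claim of control. The SAP does not say that it replaces them.

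**Conclusion.** The point holds as a defect of the protocol's procedure and as a conflict between protocol and SAP. If the protocol's success look governs, the claim in 9.2.1.3 is false for any positive correlation. For t of 0.50 to 0.571, the worst-case one-sided error is about 0.026 to 0.030 at correlations of 0.3 to 0.7, and cannot exceed 0.040 to 0.042. Correlations and information fraction are assumptions. The primary test is not affected.

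If the SAP governs, there is no inflation. What remains is to reconcile the two documents, including SAP 3.7, which still describes the alpha in its futility calculation as adjusted for the interim although a futility-only look needs no adjustment.

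**What to change.** **Preferred.** Amend the protocol (synopsis, 9.2.1 to 9.2.4, and the references to stopping for success in 3.2) to the SAP's futility-only interim and single one-sided 0.025 test, and bring the power statement in 9.2.4 into line with SAP 2.2.3. In SAP 3.7, delete the wording that calls the final alpha adjusted for the interim. The claim in 9.2.1.3 is then correct. The cost is wording, plus giving up the option to stop early for success.

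**If the success look is kept.** Restore it in the SAP. In 9.2.1.1 to 9.2.1.3 and 9.2.3.1, test every later hypothesis at 0.0147 at the look where the primary is rejected, and say on which data the secondaries are tested after an early stop. Worst-case error is then about 0.024 to 0.025, at the price of slightly lower power for those tests. This relies on an information fraction of about one half or more: at 0.4, two looks at 0.0147 give 0.0259, for the primary as well, so the fraction should be stated.

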9.2.3.2 Interim Analysis for Futility

The interim analysis for futility will also be based on the primary efficacy endpoint. The decision to stop for futility is based on the conditional probability that the study will be successful should it continue to the sample size of 105 participants in the BK ITT Population with participants being followed for 24 weeks. The calculation will assume that the final analysis will be a log-rank test

conducted at the one-sided 0.0147 level. If, at the interim analysis, the conditional probability of study success with 105 BK ITT Population participants falls below 5%, the study will stop early for futility. Enrollment and participant follow-up will then be discontinued, and the final analyses will be conducted. The futility stopping in this study is considered non-binding.

9.2.4 Sample Size Determination

Approximately 125 participants will be randomized at approximately 90 clinical sites to achieve 105 participants in the BK ITT Population (the primary efficacy analysis population), assuming 85% of randomized participants will be included in the BK ITT Population. Enrollment in the study will continue until there are 105 participants in the BK ITT Population. Participants will be randomized in a ratio to receive PSL or placebo. Assuming the median times to resolution for the placebo arm and the PSL arm are, respectively, 12 weeks and 6 weeks; time to resolution follows an exponential distribution; 24 weeks of follow-up; use of a log-rank test; one interim analysis based on the method of Pocock; control of the overall Type I error rate at the one-sided 0.025 level; 10% of participants are censored for losses to follow-up or dropout by 24 weeks; time to censoring follows an exponential distribution and is equivalent in the two arms, the study will have 83.8% power.

10 DATA MANAGEMENT AND RECORD KEEPING

10.1 Data Management

10.1.1 Data Handling

Data will be recorded at the sites on eCRFs and reviewed by the Clinical Research Associate (CRA) during monitoring visits. The CRAs will verify data recorded in the EDC system with source documents. All corrections or changes made to any study data must be appropriately tracked in an audit trail in the EDC system. An eCRF will be considered complete when all missing, incorrect, and/or inconsistent data have been accounted for.

10.1.2 Computer Systems

Data will be processed using a validated computer system conforming to regulatory requirements.

10.1.3 Data Entry

Data must be recorded using the EDC system while the study is in progress. All site personnel must log into the system using their secure username and password in order to enter, review, or correct study data. These procedures must comply with Title 21 of the CFR (21 CFR Part 11) and other appropriate international regulations. All passwords will be strictly confidential.

10.1.4 Medical Information Coding

For medical information, the following thesauri will be used:

- Medical Dictionary for Regulatory Activities (latest) for medical history and adverse events
- World Health Organization Drug Dictionary for prior and concomitant medications

10.1.5 Data Validation

Validation checks programmed within the EDC system, as well as supplemental validation performed via review of the downloaded data, will be applied to the data in order to ensure accurate, consistent, and reliable data. Data identified as erroneous, or data that are missing, will be referred to the investigative site for resolution through data queries.

The eCRFs must be reviewed and electronically signed by the Investigator.

10.2 Record Keeping

Records of participants, source documents, monitoring visit logs, eCRFs, inventory of study product, regulatory documents, and other Sponsor correspondence pertaining to the study must be kept in the appropriate study files at the site. Source data are defined as all information in original records and certified copies of original records of clinical findings, observations, or other activities in a clinical study necessary for the evaluation and reconstruction of the clinical study. Source data are contained in source documents (original records or certified copies). These records will be retained in a secure file for the period as set forth in the Clinical Study Agreement. Prior to transfer or destruction of these records, the Sponsor must be notified in writing and be given the opportunity to further store such records.

10.3 End of Study

The end of the study ("study completion") is defined as the date of the last protocol-specified visit/assessment (including telephone contact) for the last participant in the study or when the Sponsor receives the last laboratory result, whichever comes last.

11 INVESTIGATOR REQUIREMENTS AND QUALITY CONTROL

11.1 Ethical Conduct of the Study

Good Clinical Practice is an international ethical and scientific quality standard for designing, conducting, recording, and reporting studies that involve human participants. Compliance with this standard provides public assurance that the rights, safety, and well-being of study participants are protected, consistent with the principles that have their origin in the Declaration of Helsinki, and that the clinical study data are credible.

11.2 Institutional Review Board/Independent Ethics Committee

11.2.1 Institutional Review Board

The IRB will review all appropriate study documentation in order to safeguard the rights, safety, and well-being of participants. The study will only be conducted at sites where IRB approval has been obtained. The protocol, IB, ICF/assent form, advertisements (if applicable), written information given to the participants, safety updates, annual progress reports, and any revisions to these documents will be provided to the IRB by the Investigator.

Federal regulations and International Council for Harmonisation (ICH) Guidelines require that approval be obtained from an IRB prior to participation of participants in research studies. Prior to study onset, the protocol, any protocol amendments, ICFs/assent forms, advertisements to be used for participant recruitment, and any other written information regarding this study to be provided to a participant or participant's legal guardian must be approved by the IRB.

No drug will be released to the site for dosing until written IRB authorization has been received by the Sponsor.

